5.6.5. Procedural Pain

Participant assessment of procedural pain (pain during injection) on an 11-point scale ranging from 0 (no pain) to 10 (worst pain imaginable) after initial treatment will be summarized. The summary will be performed for initial treatment as described in [Table 5-10](#).

Table 5-10 **Procedural Pain Analyses**

Endpoint	Description	Timing	Methodology
Procedural pain	Summary of pain scores as continuous scale	Initial	Continuous descriptive statistics

5.6.6. Other Safety Endpoints

Other safety endpoints include the line change on Snellen visual acuity, confrontation visual fields, ocular motility assessments, and the overall converted score of FACE-Q Recovery Early Life Impact questionnaire (see [Section 6.5.5](#) and [Section 6.5.6](#)).

The number of line change based on Snellen visual acuity will be calculated using the formula below and rounded to the nearest integer. Baseline in the below formula is the pre-treatment value on or before the most recent treatment.

$$\text{Line change} = 10 \times [\log_{10} (d_{\text{baseline}}/20) - \log_{10} (d_{\text{follow-up}}/20)]$$

where d_{baseline} = denominator of the Snellen equivalent unit at baseline,

$d_{\text{follow-up}}$ = denominator of the Snellen equivalent unit at follow-up visit

Line change of visual acuity, confrontation visual fields, and ocular motility assessments assessed by the TI (or designee) will be summarized by descriptive statistics. The overall converted score of FACE-Q Recovery Early Life Impact questionnaire calculated based on the conversion table will be summarized by descriptive statistics.

5.6.7. Vital Signs

Vital sign measurements, including blood pressure (systolic and diastolic, while participant is seated), pulse rate, and temperature will be presented by a data listing.

5.6.8. Pregnancy Test Analyses

Urine pregnancy test is taken at screening, prior to every treatment (initial, touch-up and repeat), and study exit. Participants with a positive result for the Safety Population throughout the study period will be presented by a data listing.

5.7. Other Analyses

5.7.1. Subgroup Analyses

Analysis of the primary effectiveness endpoint, ACSS responder status at Month 1, will be performed separately by the following subgroups based on the observed data:

- Baseline ACSS score: 2 and 3
- Fitzpatrick skin phototype: I/II, III/IV, and V/VI

JUVÉDERM VOLITE™ XC

- Volume injected: \leq median and $>$ median
- Injection plane/technique: microdepot intradermal injection vs. other injections
- Investigational site

The median total volume injected for the initial and touch-up treatments combined on both cheeks will be calculated to determine the cut-off for the subgroup listed above. Participants who received microdepot non-intradermal injections, non-microdepot intradermal, or non-microdepot non-intradermal injections for the initial or touch-up treatment are included in the subgroup of “other” injections.

5.8. Interim Analyses

No interim analysis is planned for this study.

6. Supporting Documentation

6.1. Appendix 1: List of Abbreviations

ACSS	Allergan Cheek Smoothness Scale
AE	adverse event
AFLS	Allergan Fine Lines Scale
AESI	Adverse Events of Special Interest
ATC	Anatomical Therapeutic Chemical
CI	confidence interval
CP	control period
eCRF	electronic case report form
EI	Evaluating Investigator
GAIS	Global Aesthetic Improvement Scale
ISR	injection site response
ITT	intent-to-treat
MedDRA	medical dictionary for regulatory activities
mITT	modified intent-to-treat
RP	repeat treatment period
SAE	serious adverse event
SAP	statistical analysis plan
SI	Le Système International d'Unités (International System of Units)
SOC	system organ class
TEAE	treatment-emergent adverse event
TESAE	treatment-emergent serious adverse event
TP	treated period
VRT	VOLITE repeat treatment population
VT	VOLITE treated population
WHO	World Health Organization

6.2. Appendix 2: Changes to SAP Version 1 Analyses

The following are changes to [version 1](#) of SAP:

1. The naming of the analysis population for the sensitivity analysis of primary endpoint, ACSS responder status at Month 1 was changed from “Completer Population” to “Observed Primary Endpoint” in Section 4. The definition of this population refers to the completion of the primary timepoint visit (ie., Month 1 of CP). This naming change is aimed to avoid potential confusion with study completion.
2. The wordings of “overall converted score” were specified for the analyses of FACE-Q Satisfaction with Skin, FACE-Q Appraisal of Lines, and FACE-Q Recovery Early Life Impact in Sections 4, 5.4, 5.5 and 5.6.5 to enhance clarity and consistency with Appendix 6.5.
3. The cut-off for the of FACE-Q Satisfaction with Skin as one of the definitions for Fitzpatrick Safety Cohort was changed from 39 for the overall raw score to 69 for the overall converted score in Table 4-1.
4. The definition of “baseline” for the effectiveness and safety variables in Section 5.1 was changed to “the last non-missing assessment prior to the latter of randomization or first treatment in the control period” due to possibility of participants who were mis-treated (ie., either randomized to Volite but was not treated or randomized to Control but received Volite)
5. The multiple imputation for the primary effectiveness analysis described in Section 5.3.2 was revised to (1) include the baseline ACSS score and age in the model based on the correlation with the primary endpoint to be imputed (ie., ACSS score at Month 1 of CP) and (2) number of imputed dataset is increased from 5 to 30 to reduce variability and increase the efficiency of estimates
6. The derivation for skin hydration and analyses of following variables were added to other effectiveness analyses in Section 5.5:
 - a. raw value and change from baseline in ACSS
 - b. raw value and change from baseline in AFLS
 - c. item scores and aggregated categories for FACE-Q Satisfaction with Skin
 - d. item scores and aggregated categories for FACE-Q Appraisal of Lines
7. The analysis of ISR in Section 5.6.3 was revised to include: (1) ISR by maximum severity for summaries up to 30 days and beyond 30 days after treatment, (2) analysis of “other symptoms” based on the coded terms assigned by the Medical Safety Physician

JUVÉDERM VOLITE™ XC

8. The baseline for the analysis of visual acuity in Section 5.6.5 was specified as the pre-treatment value on or before the most recent treatment for each visit analyzed
9. A data listing to tabulate the vital sign data collected during the study is added to Section 5.6.6
10. A data listing to tabulate the positive pregnancy test during the study is added to Section 5.6.7
11. The subgroup analyses by injection technique/plane (microdepot intradermal injection vs. other injections) as requested by the FDA and by investigator site were added to Section 5.7.1
12. The inclusion of safety data collected at the unscheduled visits in the data listing was added to Section 6.4.1.2
13. The imputation algorithms for the start and end dates of medication were added to Section 6.4.2, 6.4.2.3, and 6.4.2.4 in order to determine the classification of prior vs. concomitant medications for the data listing.
14. The imputation for the missing items of FACE-Q Satisfaction with Skin, FACE-Q Appraisal of Lines, and FACE-Q Recovery Early Life Impact were added to Section 6.5.2, 6.5.4, and 6.5.6, respectively

6.3. Appendix 3: Supporting Study Information

6.3.1. Demographics

Demographic parameters (age [years]; sex; race; ethnicity) will be summarized descriptively by treatment group for the mITT populations. Age (years) were calculated relative to informed consent date.

6.3.2. Baseline and Disease Characteristics

Baseline characteristics listed below will be summarized descriptively in total and by treatment group for the mITT populations as follows:

- Weight (kg), height (cm), and BMI (kg/m²)
- Sun exposure (hours per day)
- Fitzpatrick skin phototype (each phototype, and by phototype groups [I and II, III and IV, V and VI])
- Smoking history (status, tobacco product, frequency, and duration in months)

6.3.3. Protocol Deviations

Significant protocol deviations will be identified. Unique participants reporting significant protocol deviations will be summarized in total and by treatment group for all randomized participants as described in Table 6-1.

[Listing](#) of significant protocol deviations will be provided.

Table 6-1 **Protocol Deviation Summary**

Endpoint	Description	Timing	Methodology
Significant protocol deviations	Number (%) of participants with significant protocol deviation will be summarized (All randomized)	During study period	Categorical descriptive statistics

6.3.4. Medical History

The medical and surgical history will be tabulated in data listing.

6.3.5. Prior/Concomitant Medications

Prior medication is defined as any medications taken prior to the latter of randomization date or first treatment date in the control period. Concomitant medication is defined as any medication taken on or after the latter of randomization date or first treatment date in the control period. The prior and concomitant medications will be tabulated in the data listing.

6.4. Data Handling Convention

6.4.1. Analysis Window

6.4.1.1. Effectiveness

Table 6-2, [Table 6-3](#), and [Table 6-4](#) below present the timepoints assigned for analyses and the corresponding range of study days for all the scheduled and unscheduled visits with complete dates. If a scheduled visit with incomplete date is available with no other visits with complete date during the visit window, then the visit with incomplete date may be used for analysis and the nominal visit will be used as the visit window (eg, if the only assessment collected for Month 2 visit window is on a Month 2 eCRF with incomplete date, then those data will be used for the Month 2 assessments).

If multiple assessments were taken within an analysis window, the assessment obtained on the day closest to the target day will be used; in the case of a tie, the assessment obtained on the later day will be used in the analysis.

Analysis visit windows for effectiveness endpoints are defined as follows:

If analysis date \geq reference date, then

$$\text{Analysis day} = \text{analysis date} - \text{reference date} + 1$$

If analysis date $<$ reference date, then

$$\text{Analysis day} = \text{analysis date} - \text{reference date}$$

Table 6-2 **Effectiveness Analysis Visit Definitions for Treatment Group and Control Group during Treated Period**

Scheduled Visit for Effectiveness Measure	Target Day of the Visit	Analysis Visit Window
Screening ^a	N/A	Screening visit; no more than 30 days prior to randomization
Baseline	N/A	Randomization/Initial Treatment visit
Last Treatment ^b	Day 1 of Last Treatment	Day 1
Month 1	Day 31 Post Last Treatment	Day 2 to Day 46
Month 2	Day 61 Post Last Treatment	Day 47 to Day 91
Month 4	Day 121 Post Last Treatment	Day 92 to Day 151
Month 6	Day 181 Post Last Treatment	Day 152 to Repeat Treatment Date (if applicable) or Study Exit Date, whichever is earlier

^a Participants may have screening and randomization on the same day. In such cases, only randomization visit is relevant

^b The last treatment refers to the latter of initial treatment or touch-up treatment (if applicable)

Table 6-3 Effectiveness Analysis Visit Definitions for Control Group during Control Period

Scheduled Visit	Target Day of the Visit	Analysis Visit Window
Randomization Day	Day 1	N/A
Month 1	Day 31	Day 2 to Optional Treatment Date or Study Exit Date, whichever is earlier.

Table 6-4 Effectiveness Analysis Visit Definitions for Treatment Group during Repeat Treatment Period

Scheduled Visit for Effectiveness Measure	Target Day of the Visit	Analysis Visit Window
Repeat Treatment ^a	Day 1 Repeat Treatment	Day of the Repeat Treatment
Month 1 Repeat	Day 31 Post Repeat Treatment	Day 2 to Day 76 Post Repeat Treatment
Month 4 Repeat	Day 121 Post Repeat Treatment	≥ Day 77 Post Repeat Treatment

^aNot all participants will receive repeat treatment

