5.1 Overall Design

[figure not shown]
This is a multicenter, evaluator-blind, controlled, parallel-design, prospective study of adults seeking improvement in cheek skin smoothness. Up to 20 investigational sites will enroll and follow subjects who meet the study criteria according to the study design in [Figure 5-1](#). Each site will have a PI who is responsible for the overall conduct of the study at that site and may also be the TI. The TI performs all study treatments, and the blinded EI evaluates ACSS, AFLS, and skin hydration measurements.

The study will span a total of approximately 20 months: an estimated 9 months for recruitment and 11 months for follow-up. For the treatment group, each subject's participation will encompass up to 30 days of treatment and up to 10 months of follow-up (6 months for those choosing not to receive repeat treatment at Month 6). For the control group, each subject's participation will encompass 1 month; for control subjects who opt to receive treatment, the treatment period will be up to 30 days, and the follow-up period will be up to 6 months.

Treatment group subjects receive initial treatment and optional touch-up treatment at 30 days if needed to achieve optimal correction. Follow-up visits are 3 days after each treatment (safety only) and at Months 1, 2, 4, and 6 after last treatment. Subjects exit the study at Month 6 or receive repeat treatment and are followed at Day 3 and Months 1 and 4 after repeat treatment. Control group subjects are followed for 1 month after randomization (no-treatment control period) and then either exit the study or receive optional treatment (initial and touch-up, if needed) in the delayed treatment period. Post-treatment follow-up visits are 3 days after each treatment and at Months 1, 2, 4, and 6 after last treatment.

To ensure adequate enrollment of subjects with Fitzpatrick skin phototype V and VI, up to 10 subjects may be enrolled in the Fitzpatrick V/VI safety cohort with less stringent inclusion criteria (see [Section 6.1](#)) and followed for safety only.

Figure 5-1 Study Design

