8.2 Lost to Follow-Up

A subject will be considered lost to follow-up if he/she repeatedly fails to return for scheduled visits and is unable to be contacted by the study site.

The following actions must be taken if a subject fails to return to the clinic for a required study visit:

- The site must attempt to contact the subject and reschedule the missed visit as soon as possible and counsel the subject on the importance of maintaining the assigned visit schedule and ascertain whether or not the subject wishes to end/or will continue in the study.

- Before a subject is deemed lost to follow-up, the PI/TI (or designee) must make every effort to regain contact with the subject (where possible, 3 telephone calls and, if necessary, a certified letter to the subject's last known mailing address or local equivalent methods). These contact attempts will be documented in the subject's medical record.
- If the subject continues to be unreachable, he/she will be considered to have withdrawn from the study with a primary reason of lost to follow-up.

9. Study Assessments and Procedures

- The clinical study shall not begin until the required approvals from the appropriate regulatory authorities and IRBs have been obtained.
- An unscheduled visit may occur for safety purposes (eg, evaluation of AEs or ISRs as requested by the subject and/or TI) or photographic reshoots. Applicable procedures will be performed and recorded on the eCRF.
- Throughout the study, to the extent possible, it is recommended that treatment and safety assessments for a particular subject be performed by the same TI, and effectiveness assessments (ACSS, AFLS, and hydration measurements) be performed by the same EI. If it is not possible to use the same evaluator to follow the subject, it is recommended that evaluations overlap (examine the subject together and discuss findings) for at least 1 visit.
- Where possible, subject questionnaires are to be completed prior to other assessments at each follow-up visit, with the FACE-Q questionnaires completed first.
- Safety e-diaries will ensure that subjects complete diaries on a daily basis by locking entry for prior days once they have passed.
- Study procedures and their timing are summarized in the schedule of activities ([Section 2](#)).
- Protocol waivers or exemptions are not allowed.

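### The Month 1 window for the primary endpoint has an upper day limit in the VOLITE arm but none in control, and in both arms it opens on Day 2

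*SAP*

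**What the plan says.** All effectiveness windows are in SAP Section 6.4.1.1.

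- **VOLITE, Table 6-2.** Month 1 has target Day 31 after last treatment and runs from Day 2 to Day 46. Day 1 is the later of the initial and touch-up injections. The next window, Month 2, is "Day 47 to Day 91".
- **Control, Table 6-3.** Month 1 has the same target, Day 31, counted from randomization, and runs "Day 2 to Optional Treatment Date or Study Exit Date, whichever is earlier". No day number closes it.
- **Visits admitted.** The tables apply to the "corresponding range of study days for all the scheduled and unscheduled visits with complete dates".
- **Several ratings in one window.** "the assessment obtained on the day closest to the target day will be used", with ties going to the later day. No minimum day is set, so a sole early rating is used.

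The protocol's own Month 1 visit window is -2/+7 days (Tables 2-3 and 2-4; the body of Table 2-2 was not readable in the text I had). Protocol Section 5.1 keeps Day 3 visits out of the effectiveness data: "Follow-up visits are 3 days after each treatment (safety only) and at Months 1, 2, 4, and 6 after last treatment". Protocol Section 9 allows other contacts: "An unscheduled visit may occur for safety purposes (eg, evaluation of AEs or ISRs as requested by the subject and/or TI) or photographic reshoots", with whatever procedures apply being done and recorded.

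Missing Month 1 ACSS is multiply imputed from age and baseline ACSS, by arm and cheek (SAP 5.3.2). FACE-Q at Month 1 is analysed on observed data only (SAP 5.4.1).

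**The concern.** The primary endpoint compares the arms at Month 1, so Month 1 should cover the same interval in both. At the late end it does not. The same visit delay makes a VOLITE subject missing and leaves a control observed, so who supplies observed data depends partly on arm. The late VOLITE rating does not even inform the value that replaces it, because the imputation model contains only age and baseline score. For FACE-Q the late VOLITE subject leaves the comparison and the late control stays in. The AFLS responder comparison uses the same windows.

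At the early end the rule is the same in both arms, but its effect is not. Only VOLITE subjects have just been injected. A sole rating from an early exit, an unscheduled visit or a visit attended early would be labelled Month 1 while redness, swelling, lumps or bruising may still be present. The FACE-Q items ask about the past week, so a response in the first days after injection also covers time before it.

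No planned analysis tests the windows. The tipping-point analysis in SAP 5.3.3 varies only values classed as missing, and the Observed Primary Endpoint analysis takes its members from the same windows.

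**Working it through.** **The plan's own figure.** Inputs from SAP Section 3: 112 VOLITE and 56 control, responder rates 80% and 40%, 2-sided Fisher's exact test at 5%. Summing the two binomial distributions over all tables that reject gives power of 99.91%, against 99.9% stated. The randomization target also reproduces: (112 + 56) / (1 - 0.20) = 210, which at 2:1 is 140 and 70.

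**Day arithmetic.** Analysis day = analysis date - reference date + 1.

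- Protocol window: 31 - 2 = Day 29 to 31 + 7 = Day 38, which is 10 days.
- SAP VOLITE window: Day 2 to Day 46, which is 46 - 2 + 1 = 45 days.
- SAP control window: from Day 2 with no fixed end. A control who declines treatment exits at the Month 1 visit, so even a very late visit lies inside it.

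**The same sole rating in each arm** (control untreated and still in the study):

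| Day of rating | VOLITE | Control |
|---|---|---|
| 5 | observed Month 1 | observed Month 1 |
| 31 | observed Month 1 | observed Month 1 |
| 50 | Month 2; Month 1 missing | observed Month 1 |
| 80 | Month 2; Month 1 missing | observed Month 1 |

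The arms diverge from Day 47, which is 47 - 38 = 9 days past the protocol limit.

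**The SAP's boundary logic.** Internal limits are midpoints of neighbouring targets: (31 + 61)/2 = 46, (61 + 121)/2 = 91, (121 + 181)/2 = 151 and, in Table 6-4, (31 + 121)/2 = 76. The same logic between Day 1 and Day 31 gives (1 + 31)/2 = 16.

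**Illustrative size.** The documents give no shares, so these are assumptions.

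- Late visits: if 5% of Month 1 visits fell after Day 46, then 0.05 x 140 = 7 VOLITE subjects would be imputed, while 0.05 x 70 = 3.5 controls would be analysed as observed.
- Early VOLITE ratings: shift = share x (early rate - 80%). With a 10% share, an early rate of 60% gives -2.0 points and 95% gives +1.5. With a 2% share the range is -0.4 to +0.3.
- Late control ratings: shift = share x (late rate - 40%). With a 10% share and late rates of 20% to 60%, the range is -2.0 to +2.0 points.
- Early VOLITE and late control extremes together: 40 - 2.0 - 2.0 = 36.0 points to 40 + 1.5 + 2.0 = 43.5 points.

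**Power cost of a common window.** If a share of Month 1 ratings is lost in each arm and excluded, Fisher power at 80% versus 40% is 99.9% for 5% lost (106/53), 99.8% for 10% (101/50) and 99.5% for 20% (90/45).

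**The case against.** The windows follow a recognisable convention: contiguous intervals, midpoints as limits, and the first window opening on Day 2 in all three tables. Untreated controls have no Month 2 visit, so there is no next target from which to form an upper midpoint. That explains the difference but does not make the intervals comparable.

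The early route is narrow. Day 3 visits are safety only, unscheduled visits are not said to include an evaluator rating, and any rating nearer Day 31 within the window displaces an early one. The late route needs a visit well past the protocol limit, and an untreated control has no treatment effect to wane. The tipping-point analysis does cover late VOLITE subjects classed as missing. These points stand, and they limit the number affected.

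A reader might infer that swelling makes early VOLITE ratings look smoother, so that the window inflates the VOLITE rate. No passage says that swelling improves the ACSS, and the listed injection site responses include lumps/bumps, bruising and redness, which could worsen visual texture.

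A reader might also put a figure on this: 1 to 4 early-rated subjects of 140, all responders, would add 1/140 = 0.7 to 4/140 = 2.9 points. The count has no source in the documents. The gain is also gross: it requires that these subjects would otherwise be non-responders, as under the protocol's missing-data rule (Section 10.3.1.2). If they would respond, or be imputed, at about 80%, the net gain is 0.2 x 0.7 = 0.1 to 0.2 x 2.9 = 0.6 points.

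**Conclusion.** The concern holds as a matter of comparability. The plan gives Month 1 a different upper limit in each arm, and it lets a sole rating from the days just after injection stand for Month 1. Both follow directly from Tables 6-2 and 6-3.

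The number of subjects affected is unknown and probably small, and the direction of any bias is uncertain. The documents do not support reading this as a bias in favour of VOLITE or as a threat to the primary result. Under the assumed shares and rates above, the early VOLITE and late control ratings leave a planned 40-point difference between 36.0 and 43.5 points. That range omits the effect of imputing late VOLITE subjects, which the tipping-point analysis addresses. The change is worth making because this is a pivotal comparison and the remedy is cheap.

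**What to change.** In SAP Tables 6-2 and 6-3, define one Month 1 window with the same lower and upper day in both arms, for example Day 16 to Day 46 (target Day 31 +/-15). Count it from last treatment for VOLITE and from randomization for control. In control it should also end at the optional injection, keeping ratings taken before that injection on the optional treatment date. State that ratings outside the window are missing at Month 1 in both arms and go to the planned handling for each endpoint.

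Add a sensitivity analysis of the primary endpoint limited to ratings within the protocol's -2/+7 days (Day 29 to Day 38), since Day 16 to Day 46 is still wider than the visit schedule.

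The change is table wording plus one extra analysis. Table 5-1 should be checked at the same time, because the end of the control period depends on which assessment is taken as Month 1. The downside is that a few very early ratings and a few late control ratings become missing. The power calculation above shows that this costs almost nothing.
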